1. Using CMA, the individual coronary arteries were marked as high ^{18}F -NaF if $\text{CMA} > 1.56$. We assessed the burden of activity on a per-vessel and per-patient level. To allow a per-patient analysis, we added the CMA activity of all major epicardial vessels ($\text{CMA}_{\text{total}}$). For TBR, PET uptake was quantified based on the CCTA lesion position, with lesions categorized as ^{18}F -NaF-positive ($\text{TBR}_{\text{MAX}} \geq 1.3$) or ^{18}F -NaF-negative ($\text{TBR}_{\text{MAX}} < 1.3$).

BENEFITS

Evolocumab is clinically indicated for patients with ASCVD as defined in the inclusion criteria. We are not aware of any direct benefit for subjects from quantification of plaque volumes or microcalcification.

OFF-LABEL USE OF SODIUM FLUORIDE F-18-NaF

Sodium Fluoride F-18 Injection is a radioactive diagnostic agent for PET approved to use in imaging of bone to define areas of altered osteogenic activity. Sodium Fluoride F-18 Injection is not, however, approved for the indication of cardiac imaging.

The prescribed dose for an adult bone study is 300-450 MBq (approved dose for bone scanning). This study will employ a lower dose of 250 MBq. This follows the recommendation that the dose be minimized consistent with the objectives of the procedure and the nature of the radiation detection devices employed. The use of this lower dose has been shown to be effective in previous studies conducted at CSMC.

The ^{18}F -NaF for this study will be manufactured by PetNet (Culver City, CA) and will be received by our radiopharmacy in the S. Mark Taper Imaging Center, Nuclear Medicine division. Our radiopharmacist will prepare the doses for administration for the cardiac imaging procedures.

Use of ^{18}F -NaF in this study does not involve a route of administration, dose, patient population, or other factor that significantly increases the risk (or decreases the acceptability of the risk) associated with the use of ^{18}F -NaF for the approved use in bone scanning.

The investigators have no intention of reporting data from this study to the FDA for change in indications or labeling.

RISKS

18F-NaF PET: According to the package insert, there are no contraindications and no adverse reactions have been reported for Sodium Fluoride F 18 Injection based on a review of the published literature, publicly available reference sources, and adverse drug reaction reporting systems. As with any injectable drug product, allergic reactions and anaphylaxis may occur. This research procedure is being conducted in a clinical setting and emergency resuscitation equipment and personnel are immediately available.

As with other radiopharmaceuticals, this injection has the potential to cause harm to an unborn child. Pregnant women will not be enrolled. Department policy states that all females of child bearing age (10-60yo) are screened to determine pregnancy status. If the female volunteer is of child bearing age and the first day of their last menstrual cycle is not within the past 30 days, we will administer a one-step HCG urine test (QuickVue®, Quidel Corp) in the department to determine their pregnancy status. To minimize the risks to a nursing infant, it is recommended that mothers interrupt nursing for at least 24 hours.

CCTA: The physical procedure of CCTA and administration of intravenous contrast are generally considered low-risk in patients without significant renal dysfunction and other contraindications to intravenous contrast. We will be performing the CCTA at least 48 hours after the initial dye load in the cath lab (if they have been enrolled from the cath lab), the risk of renal dysfunction is minimal.

Beta-Blocker and Nitroglycerin: Administration of metoprolol and sublingual nitroglycerin is associated with minimal risk since patients with clinical contraindications will be excluded.

Radiation: Estimated total radiation exposure from 18F-NaF is approximately 0.81 Rem from the combined 18F-NaF and associated attenuation scans. This calculation is based on 0.0027 Rem/MBq dose equivalent for ¹⁸F-NaF and 0.138 Rem average radiation for cine-CT attenuation scan [22], and approximately 0.8 rem from the coronary CTA.

The study includes a baseline and a final 18F-NaF as well as a baseline and a final CCTA. The baseline CTA may be eligible if done clinically within 60 days prior to enrollment.

Evolocumab:

Hypersensitivity reactions (e.g., rash, urticaria) have been reported in patients treated with evolocumab, including some that led to discontinuation of therapy. If signs or symptoms of serious allergic reactions occur, discontinue treatment with evolocumab, treat according to the standard of care, and monitor until signs and symptoms resolve. Please see section 6 of the appendix [Repatha prescribing information.pdf](#).

PRIMARY ENDPOINT

1. Change in noncalcified coronary artery plaque volume from baseline to month 18 of treatment with Evolocumab.
2. Change in plaque composition (low density non-calcified and calcified) from baseline to month 18 of treatment with Evolocumab.

STATISTICAL ANALYSIS PLAN

For all statistical analyses, two-sided tests will be conducted and p-values < 0.05 will be considered significant. Continuous variables will be presented as mean \pm standard deviation (SD) or median (interquartile range) as appropriate. Annualized rate of change in total plaque volume, and the volume of non-calcified plaque, specifically, low density non calcified plaque components will be analyzed. Mean values will be compared using a paired Student's t-test median values will be compared using the Wilcoxon rank-sum (Mann-Whitney) test. The relationship between decrease in LDL and changes in plaque volume and individual plaque components per year will be evaluated after adjusting for the effects of confounding variables including age, diabetes, hypertension, smoking, family history of premature coronary artery disease, statin use, baseline LDL and baseline plaque volume. Reproducibility of measurements of, volume of plaque components and total plaque volume will be assessed using intra-class correlations and coefficients of variation.

SAMPLE SIZE POWER CALCULATIONS

In a study of 116 patients who underwent sequential CTA, we observed a reduction in total plaque volume and NCPV among patients who experienced a reduction in LDL of >10% of their baseline LDL level under the influence of statins alone. Based on this preliminary work, we expect to detect a difference of at least 50mm³/year in non-calcified plaque volume (Δ NCPV = NCPV_{pre-treatment} – NCPV_{post-treatment}) among patients who were treated with evolocumab. From our data, we estimate the population standard deviation for measurement of (Δ NCPV/year) to be 115mm³. Using a paired t-test with a power of 80% and an alpha value of 0.05, we would need 44 patients in our treatment group.

After accounting for approximately 10 patients who might withdraw from the study, we propose to enroll 55 patients in our treatment group.

INSTITUTIONAL REVIEW BOARD (IRB)

Prior to study initiation and when amended, the protocol and any applicable advertisement for patient recruitment will be submitted for review and approval to the IRB charged with this responsibility. Site personnel must provide reports of the progress, or completion, termination or discontinuation of the study to the IRB at appropriate intervals. The investigator will verify that each subject has consented, in writing, to direct access to his/her original medical records for trial-related monitoring, audit, IRB/IEC review, and regulatory inspection.

DATA COLLECTION AND MANAGEMENT

All information from the 18F-NaF PET scan and CCTA scan performed while the subject is at CSMC may be used for research analysis including the actual images, acquisition parameters of the imaging protocol, any information collected at the time of the test, and information from the patient's medical record.

DATA AND SAFETY MONITORING

All suspected unexpected serious adverse reactions (SUSARs) related or possibly related to evolocumab and their follow-up reports will be reported to Amgen within 24 hours of submission to the regulatory agency, IRB or IEC. A copy of any safety report involving an Amgen drug (e.g. evolocumab) submitted to the regulatory agency, IRB or IEC, will be faxed to Amgen, within 24 hours of such submission.

The sponsor will report all pregnancies and pregnancies occurring in the partner of a patient participating in the study or potential infant exposure through lactation within 10 calendar days of sponsor's awareness to Amgen.

DATA REPORTING

Routine reporting of recruitment, protocol compliance and data collection is planned annually to the IRB once recruitment begins. Occurrence of safety incidences including adverse events are reported according to CSMC compliance requirements. The investigators will provide direct access to source data/documents for trial-related monitoring, audits, IRB/IEC review, and regulatory inspection. The investigators have no intention of reporting data from this study to the FDA for change in indications or labeling.

PATIENT CONFIDENTIALITY

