Treatment with the PCSK9 inhibitor, evolocumab has been shown by intravascular ultrasound to be associated with a reduction of percent atheroma volume after 1.5 years of treatment; however, it is not known how evolocumab affects specific coronary plaque types and plaque inflammation [6, 7]. Although intravascular ultrasound (IVUS) can provide quantitative measurements of total atheroma volume, it is an invasive technique with associated procedural risks and therefore not practical for routine clinical monitoring of response to medical therapy. Quantitative assessment of changes in plaque burden, plaque composition and vascular inflammation in response to treatment with a PCSK9 inhibitor with noninvasive imaging (CCTA and positron emission tomography (PET) can provide a comprehensive assessment of pathophysiologic changes before and during treatment.

Our group has developed and extensively validated a semiautomatic method of comprehensive measurements of coronary plaque burden and plaque composition in the entire coronary artery tree on CCTA (Autoplaque) [8-12]. Among the many Autoplaque measurements are noncalcified plaque volume, low density non calcified plaque volume, the latter representing the necrotic core. We have shown strong correlation of noncalcified plaque volume with IVUS [10] and have documented excellent reproducibility of the various plaque measurements [12]. In 116 patients having serial studies over 3.5 ± 1.6 years, we have preliminary evidence that a 10% reduction in LDL is associated with an interval reduction in the volumes of all components of non-calcified plaque including adverse plaque characteristics associated with plaque instability and predictive of future cardiac events [13, 14].

With PET, our co-investigators have shown that microcalcification activity within coronary arteries and the aorta-reflecting the rate of deposition of calcium-can be assessed by 18F sodium fluoride

(NaF) PET. This process is considered to be governed by the degree of plaque inflammation, and as such another marker of plaque vulnerability [15]. Thus, 18F NaF PET allows the assessment of the effect of therapy on a measurement related to plaque inflammation.

STUDY DESIGN

This is an early development, single-arm, prospective, open-label study of evolocumab injection in patients with calcified plaque in the coronary artery detected by CCTA. Fifty-five (55) evaluable subjects will be enrolled in the study.

OBJECTIVES

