1. To test the hypothesis that PCSK9 (proprotein convertase subtilisin kexin type 9) inhibitor, evolocumab, reduces the volume of noncalcified plaque in coronary arteries as measured by coronary computed tomography angiography (CCTA)
2. To determine the components of non-calcified coronary artery plaque that are affected by treatment with evolocumab.
3. To determine if lipid lowering with evolocumab is associated with changes in microcalcification in atherosclerotic plaque as measured by F18-NaF PET

SPECIFIC AIM

To quantify changes in coronary plaque volumes and plaque composition in patients treated with evolocumab.

Hypothesis: Patients treated with evolocumab demonstrate a reduction of coronary non-calcified plaque volume, including a preferential reduction in volume of low density non-calcified plaque components

EXPLORATORY AIMS

To evaluate whether patients treated with evolocumab demonstrate reduced microcalcification activity in the coronary arteries as assessed by 18F NaF.

Hypothesis: Treatment with evolocumab will be associated with reduced rate of coronary plaque inflammation which may be detected as a reduction in the rate of microcalcification activity.

SUBJECT DESCRIPTION

Treatment Group

Inclusion Criteria

Treatment group will be comprised of 55 adult male and female patients who satisfy the following enrollment criteria:

- Evidence by CCTA of noncalcified coronary artery plaque ($>440 \text{ mm}^3$)
- On-label indications for evolocumab treatment which includes the following criteria:
Those who have established cardiovascular disease defined as acute coronary syndrome, history of myocardial infarction, stable angina or unstable angina, coronary or other arterial revascularization, stroke, transient ischemic attack, or peripheral arterial disease presumed to be of atherosclerotic origin.
- Non-calcified plaque (NCP) volume of 250 mm^3 or more in any single plaque in patients who do not have a total NCP $>440 \text{ mm}^3$

Exclusion Criteria

- Creatinine $> 1.5 \text{ mg/dL}$ prior to imaging
- History of allergy to iodine contrast agents
- Allergy to evolocumab or any other ingredients contained in study drug, including latex
- Pregnancy
- Women who are breastfeeding
- Active atrial fibrillation
- History of coronary artery bypass graft
- Inability to lie flat
- Inability or unwilling to give informed consent
- Major illness or life expectancy $<1 \text{ year}$

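### Noncalcified plaque volume and two plaque-composition measures share the primary endpoint at an unadjusted 0.05, with no testing order, alpha split or success rule

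*Combined protocol and SAP*

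**What the plan says.** The Primary Endpoint section has two numbered items. The first is "Change in noncalcified coronary artery plaque volume from baseline to month 18 of treatment with Evolocumab". The second is "Change in plaque composition (low density non-calcified and calcified) from baseline to month 18 of treatment with Evolocumab", which brings in two further measures. The Statistical Analysis Plan sets one rule for all analyses: "two-sided tests will be conducted and p-values < 0.05 will be considered significant". On the outcomes themselves it says: "Annualized rate of change in total plaque volume, and the volume of non-calcified plaque, specifically, low density non calcified plaque components will be analyzed". That sentence includes total plaque volume, which is not a listed endpoint, and does not name calcified plaque, which is.

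The Sample Size section is built on NCPV change per year alone and concludes that "we would need 44 patients in our treatment group". Under Objectives, the first is a hypothesis test on NCPV and the second is "To determine the components of non-calcified coronary artery plaque that are affected by treatment with evolocumab". The Specific Aim hypothesis is a fall in NCPV, "including a preferential reduction in volume of low density non-calcified plaque components". Neither section predicts a change in calcified volume.

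No section gives a testing order, an alpha allocation, a multiplicity adjustment or a definition of a positive study.

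**The concern.** Three measures sit under one primary heading, each covered by the same 0.05 rule. The numbering 1 and 2 is not described as a testing order. If NCPV were not significant but low-density plaque were, the plan would not stop the low-density result from being presented as a met primary endpoint. On that use, the 5% error rate does not describe the primary claim. Nor does the 80% power, which was calculated for NCPV only.

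The membership of the primary set is also unsettled. Calcified plaque is listed as primary without a hypothesis and without a place in the annualized-change sentence, so a reader cannot tell whether two or three measures are to be tested. That mismatch stands whatever success rule is assumed.

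**Working it through.** **Inputs.** From the Sample Size section: difference 50 mm³/year, SD 115 mm³, paired t-test, alpha 0.05, power 80%. From the Statistical Analysis Plan: two-sided 0.05 for every test. The documents give no correlations between the changes in the plaque measures, so a common correlation from 0.3 to 0.9 is assumed.

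**1. The plan's own figure.** With n = 44 the noncentrality is (50/115) × √44 = 0.4348 × 6.633 = 2.884, and the critical t on 43 degrees of freedom is 2.017. The noncentral t gives power 80.5%. At n = 43 it is 79.5%, so 44 is the smallest sufficient number. The stated sample size reproduces.

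**2. Chance of at least one false positive if any one result counts.** For independent tests this is 1 − 0.95² = 9.75% for two and 1 − 0.95³ = 14.3% for three. For correlated measures, paired t-tests were simulated at n = 44 with all true changes zero (200,000 runs):

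| Assumed correlation | 0.3 | 0.5 | 0.7 | 0.9 |
|---|---|---|---|---|
| NCPV and low-density, two-sided | 9.4% | 9.1% | 8.4% | 7.0% |
| Calcified added, two-sided | 13.6% | 12.6% | 11.0% | 8.4% |
| NCPV and low-density, reductions only | 4.8% | 4.5% | 4.2% | 3.5% |

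The comparator is 5% for the first two rows and 2.5% for the third. Repeat runs differ by a few tenths of a percentage point at most.

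**3. The other two readings.** If NCPV alone decides, the error is 5.0% (2.5% for reductions). If all three results are required, it is at most 2.2% over the same correlations. Neither is inflated.

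**4. Cost of the possible remedies.**
- *Fixed sequence, NCPV first.* NCPV keeps alpha 0.05, n = 44 and 80.5% power. If low-density plaque had the same standardized effect, 50/115 (an assumption), the chance that both are significant is 67% at correlation 0.3 and 75% at 0.9. Tested alone, low-density plaque would have about 80%.
- *Bonferroni over two measures.* Alpha is 0.05/2 = 0.025, and 80% power for NCPV then needs 53 evaluable patients. NCPV power is 71.2% at 44, 72.3% at 45 and 81.8% at 55. All three sizes matter because the documents differ: Study Design speaks of 55 evaluable subjects, while the Sample Size section allows about 10 withdrawals from 55 enrolled, leaving 55 − 10 = 45.

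**The case against.** The strongest reply is that the hierarchy is already plain. Objective 1 tests a hypothesis on NCPV, whereas objective 2 only asks which components are affected. Low-density plaque is hypothesised as part of the NCPV reduction, and NCPV is both the first endpoint and the only powered one. This stands as far as it goes: NCPV is the lead, and a reader who inferred that the plan leaves its main variable unidentified would be wrong. But the plan does not say that the second item is secondary, and it places it under the same primary heading.

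A reader might also infer that the study has a false-positive rate of up to 14%. The documents do not support that. The figure needs an any-one-wins rule that appears nowhere, and it counts calcified plaque as a planned primary test although only the general 0.05 sentence reaches it. The second item is also worded as composition; treating its parts as volumes rests on the quantitative CCTA measurements section. A reductions-only figure for three measures would be unsupported too, because no direction is hypothesised for calcified plaque. For the two hypothesised measures, the reductions-only rate exceeds its own 2.5% comparator but stays below the nominal 5%.

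Finally, the stakes are limited. Study Design states: "This is an early development, single-arm, prospective, open-label study of evolocumab injection". Data Reporting disclaims any intention to seek a labeling change. That lowers the weight but does not remove the gap, since the plan still sets a formal significance rule and is powered on it.

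**Conclusion.** The concern holds as an unstated hierarchy within the primary endpoint, together with endpoint and analysis lists that disagree. The size depends on the success rule. If any one result counts, the two-sided error is about 7% to 9.5% for the two hypothesised measures and 8% to 14% with calcified plaque added, against 5%. Counting only reductions in the two hypothesised measures, it is 3.5% to 4.8% against 2.5%. These figures assume n = 44, true changes of zero and correlations of 0.9 to 0.3. There is no inflation if NCPV alone decides or all results are required. The sample-size arithmetic is correct. The point should be fixed, but its weight is modest.

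**What to change.** - Name change in NCPV as the single primary endpoint, at two-sided 0.05.
- Test low-density noncalcified plaque at two-sided 0.05 only if NCPV is significant.
- Report calcified and total plaque volume as exploratory or supportive, and make the endpoint list and the analysis sentence name the same measures.
- Date the amendment. The image-analysis sections are written in the past tense. If scan order is already unblinded, label the order post hoc and report the composition p-values as descriptive, because a post hoc order does not restore error control.

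The endpoint is worded as change to month 18, while the sample size and analysis use change per year. Choosing between them is a separate question that this fix does not need to settle.

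The amendment adds no patients and leaves NCPV's alpha and power as calculated. The price is that composition results cannot be claimed as confirmatory if NCPV fails. A Bonferroni split over two measures would avoid that price, but it reaches 80% power for NCPV only if the evaluable number is near the 55 in Study Design rather than the 44 or 45 in the Sample Size section.

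### The SAP compares medians with the unpaired Wilcoxon rank-sum test, although every baseline-to-month-18 comparison in this single-arm trial is within-patient

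*Combined protocol and SAP*

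**What the plan says.** The Study Design section of the combined protocol and SAP states: "This is an early development, single-arm, prospective, open-label study of evolocumab injection". There is no comparator group.

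Under Primary Endpoint, the first item is "Change in noncalcified coronary artery plaque volume from baseline to month 18 of treatment with Evolocumab". The second is the change in plaque composition over the same period. Both are differences within a patient.

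The Statistical Analysis Plan section then says:

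- Continuous variables are presented as mean with SD or as "median (interquartile range) as appropriate".
- The quantities to be analysed include "Annualized rate of change in total plaque volume, and the volume of non-calcified plaque".
- For means: "Mean values will be compared using a paired" Student's t-test.
- For medians, in the same sentence: "median values will be compared using the Wilcoxon rank-sum (Mann-Whitney) test".
- For all analyses, "two-sided tests will be conducted and p-values < 0.05 will be considered significant".

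Sample Size Power Calculations is also on a paired basis: "Using a paired t-test with a power of 80% and an alpha value of 0.05", giving 44 patients. The signed-rank test is not named anywhere.

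**The concern.** The rank-sum test compares two independent samples. The added name Mann-Whitney leaves no room to read it as the paired Wilcoxon test. In this trial it can be applied in two ways, and neither suits the endpoint:

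- **Baseline volumes against month-18 volumes.** The two sets come from the same patients. The test treats them as separate groups, so stable differences between patients in plaque volume enter the error term.
- **Annualized change.** One arm gives one sample of changes, so the test has nothing to compare it with.

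The SAP therefore pairs the comparison of means and the sample size but not the comparison of medians. Since nothing says when medians take over, the unpaired test could be used on a primary endpoint, and a real reduction in plaque could then be missed.

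**Working it through.** **Inputs from Sample Size Power Calculations.** Expected change 50 mm³/year, SD of the change 115 mm³/year, two-sided alpha 0.05, power 80%, n = 44. Over 18 months the same figures are 50 × 1.5 = 75 mm³ and 115 × 1.5 = 172.5 mm³. The ratio is the same on either scale: 50/115 = 75/172.5 = 0.435.

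**Input not in the documents.** The correlation ρ between baseline and month-18 volume is not given, nor is the SD of volume across patients at a visit. ρ is therefore an assumption, varied from 0 to 0.9.

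**Step 1: reproduce the plan's figure.** For the paired t-test, power comes from the noncentral t distribution with n − 1 degrees of freedom and noncentrality 0.435 × √n. It is 0.795 at n = 43 and 0.805 at n = 44. The stated 44 is reproduced.

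**Step 2: what ignoring the pairing does.** Let σ be the SD across patients at each visit, equal at both visits. The variance of a patient's change is 2σ²(1 − ρ). A test that treats the visits as independent works as if it were 2σ², which is larger by a factor of 1/(1 − ρ): 2 at ρ = 0.5 and 5 at ρ = 0.8. Holding the SD of change at the plan's value gives σ = 172.5/√(2(1 − ρ)). At ρ = 0.5, for example, σ = 172.5/√1 = 172.5 mm³.

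**Step 3: simulation.** Paired normal data, n = 44, mean change 75 mm³ for power and 0 for type I error, 20,000 runs per cell (Monte Carlo standard error at most 0.4 percentage points). Signed-rank power was about 0.79 at every ρ.

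| ρ (assumed) | σ at each visit, mm³ | Rank-sum power | Rank-sum type I error |
|---|---|---|---|
| 0 | 122 | 0.79 | 5.0% |
| 0.3 | 146 | 0.67 | 2.2% |
| 0.5 | 173 | 0.50 | 0.7% |
| 0.6 | 193 | 0.38 | 0.2% |
| 0.7 | 223 | 0.23 | 0.1% |
| 0.8 | 273 | 0.08 | 0.01% |
| 0.9 | 386 | 0.003 | 0% |

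At ρ = 0.5 the relative loss is (0.79 − 0.50)/0.79 = 37%, rather more than a third. At ρ = 0.6 it is (0.79 − 0.38)/0.79 = 52%. A separate simulation on the annual scale agreed within simulation error.

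**Step 4: other shapes of data.**

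- *Heavy-tailed changes* (t distribution with 5 degrees of freedom, same SD, 10,000 runs): rank-sum power is 0.83, 0.51, 0.23, 0.08 and 0.004 at ρ = 0, 0.5, 0.7, 0.8 and 0.9. Signed-rank power is 0.86 to 0.88.
- *Right-skewed patient levels* (exponential) with normal changes: rank-sum power is about 0.65 to 0.67 at ρ = 0.5, 0.48 at 0.7 and 0.31 to 0.32 at 0.8. Signed-rank depends only on the changes, so it stays at about 0.79.

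**Step 5: is there a two-group comparison the test could serve?** The SAP plans an adjusted analysis of LDL reduction against plaque change across patients. The section on diagnostic evaluation of CMA and TBRmax defines high and positive tracer-uptake categories. Neither is linked to the rank-sum test. If one had been meant, the within-patient median comparison would be left with no test at all.

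**The case against.** The strongest reply has four parts.

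1. **It is a fallback and may be a slip.** The paired t-test stands in the same sentence, the sample size rests on it, and signed-rank may have been meant. This limits the seriousness. The named test is still the specified analysis, and nothing confines medians to minor variables.

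2. **The severe power figures assume normal data, while medians would be used for skewed data.** The entry criterion of more than 440 mm³ of noncalcified plaque (or 250 mm³ in a single plaque) makes right-skewed volumes plausible. This stands in part: with exponential patient levels the loss is smaller, 0.48 instead of 0.23 at ρ = 0.7. It remains large against about 0.79.

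3. **Signed-rank has conditions too.** It tests a median or mean change only if the changes are roughly symmetric. In an extreme case with shifted-exponential changes, it had power of about 0.58 against 0.89 for the paired t-test, and it rejected about 20% of the time when the mean change was zero, because it was no longer testing the mean. This is a fair caution about relying on signed-rank for skewed changes. It does not make an independent-samples test right for paired data.

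4. **The risk is not only a missed effect.** The rank-sum test alone is conservative under positive correlation, but choosing between tests after seeing the data can produce false positives. This is correct and is a reason to fix the rule of choice as well.

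The plan also reports results per lesion. The calculations here cover one value per patient and do not address several lesions within a patient.

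**Conclusion.** The concern holds: the test named for medians does not fit the design, and it contradicts the paired t-test beside it and the paired sample size.

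The size of the harm is conditional. It arises only if the median route is taken, and it depends on a correlation that the documents do not give. With no correlation there is practically no loss. Positive correlation is to be expected for serial measurements in the same patient; under normal data, rank-sum power then falls from about 0.79 to 0.50 at ρ = 0.5 and 0.23 at ρ = 0.7, and under skewed patient levels to about 0.65 to 0.67 and 0.48. These figures use the plan's change and SD, 44 patients and equal SDs at both visits.

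The sample size and the paired t-test are sound as they stand. This should be corrected, but it does not undermine the design.

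**What to change.** In the Statistical Analysis Plan section, replace the rank-sum (Mann-Whitney) test with the Wilcoxon signed-rank test on within-patient changes, or annualized changes, with one value per patient. Keep the rank-sum test only for a two-group comparison that the SAP specifies in advance, if there is one.

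It is also advisable to name the paired t-test used for the sample size as the primary test for noncalcified plaque volume, or else to state in advance the criterion for moving to medians. The choice of test then cannot depend on the results. A short note that signed-rank assumes roughly symmetric changes would help whoever applies the rule.

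The correction of the test is one line of SAP wording and needs no further patients or data. Under normal changes, signed-rank gives up about one to two percentage points of power against the paired t-test (about 0.79 against 0.805 at n = 44).
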